13.0 Recruitment and Consent

13.1 Please describe the recruitment process, including how subjects will be identified and selected for the study.

Providers will ask their patients if they are interested in being referred to the research department. If the subject agrees, the provider will provide the research department their name and phone number and/or give the patients the contact information for the research department. We will also post advertisements around the hospital. Some patients may be patients of the PI or AI; however, they will have another study staff recruit their patients to prevent any misconception of coercion or undue influence.

13.2 Compensation for Participation:

Subjects will not be paid for their participation.

13.3 Please describe the pre-screening process. If no pre-screening, enter Not Applicable in the text editor

N/A

13.4 Consent Process: Revised Common Rule, Section 219.116: General requirements for informed consent, whether written or oral, are set forth in this paragraph and apply to consent obtained in accordance with the requirements set forth in paragraphs (b) through (d) of this section. Broad consent may be obtained in lieu of informed consent obtained in accordance with paragraphs (b) and (c) of this section only with respect to the storage, maintenance, and secondary research uses of identifiable private information and identifiable biospecimens.

Are you requesting a waiver or alteration of informed consent?

Yes No

Please explain the consent process:

Informed Consent and HIPAA Authorization will be sought in advance of any screening and study-related procedures from each prospective study subject and appropriately documented in accordance with 32 CFR 219.117. The subject may decline to consent without prejudice. At the subjects' discretion, they may take the ICD home to discuss further with family members or another physician prior to making a decision. If the subject consents, a copy of the signed ICD and HIPAA Authorization Document will be given to the subject.

13.5 DoDI 3216.02 requires an ombudsman to be present during recruitment briefings when research involves greater than minimal risk and recruitment of Service members occurs in a group setting. If applicable, you may nominate an individual to serve as the ombudsman.

N/A
 Propose ombudsman

13.6 Withdrawal from Study Participation:

Explain the process for withdrawal and specify whether or not the subjects will be given the opportunity to withdraw their data their data/specimens in the event they wish to withdraw from the study

If a participant first agrees to participate and then changes their mind, they are free to withdraw consent and discontinue participation at any time. Their decision will not affect their ability to receive medical care and will not be penalized or lose any benefits to which they would otherwise be entitled. There are no risks from withdrawing. They will be advised in the Informed Consent process that if they decide to withdraw from the study early, we will ask them to discuss their decision with the study staff. The researcher may withdraw them from the study prior to the study's end without their consent for one or more of the following reasons: Failure to follow the instructions of the researchers and study staff. The researcher decides that continuing their participation is not in their best interests. The study is cancelled. Other administrative reasons. Unanticipated circumstances. They become Pregnant or begin lactating. If they lose their status as a military health care beneficiary, they can no longer be included in the study.

Patients will be discontinued from the study if intraoperative complications or concerns are noted PRIOR to capsular tension ring insertion.

Intraoperative complications may include:

- capsular bag tears or rents
- anterior vitrectomy
- phacodonesis
- damaged zonules
- use of non-toric intraocular lens
- other intraoperative complications that would influence capsule or lens positioning or stability

Patients will continue to be enrolled in the study to further characterize the safety of the investigational device and treatment if intraoperative complications occur DURING OR AFTER the point of possible capsular tension ring insertion. This includes secondary surgical interventions such as repositioning of the IOL. These eyes will not be included in the data analysis after this point.

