9.0 Study Details

9.1 Key Words:

Provide up to 5 key words that identify the broad topic(s) of your study

Capsular Tension Ring; intraocular lens; ophthalmology; cataract surgery; toric lens

9.2 Background and Significance:

Include a literature review that describes in detail the rationale for conducting the study. Include descriptions of any preliminary studies and findings that led to the development of the protocol. The background section should clearly support the choice of study variables and explain the basis for the research questions and/or study hypotheses. This section establishes the relevance of the study and explains the applicability of its findings

This study has the potential to improve surgical outcomes in cataract surgery with toric intraocular lenses. Twenty million people have cataract surgery annually worldwide, and approximately 30% have visually significant astigmatism and are candidates for toric intraocular lenses. In turn, postoperative uncorrected visual acuity depends on the toric axis. For every degree of rotation away from the target axis, there is a 3.3% decrease in the astigmatism correction. This means that if the toric intraocular lens is rotated 10%, there is a 30% decrease in the correction of astigmatism. This generally negates the benefit of the toric lens, requiring correction for the refractive error.¹⁻⁴ Implanting a capsular tension ring is a simple surgical technique that has the potential to reduce toric rotation and improve refractive error.

Instead of a round cornea (like a basketball), some patients have a more oblong cornea (like a football). This is called astigmatism, and it can affect whether patients require glasses or other refractive correction in order to see clearly. Toric intraocular lenses are FDA-approved for use during cataract surgery to correct refractive error due to corneal astigmatism. This improves patients' refractive error and makes it less likely that they will need glasses after cataract surgery. These intraocular lenses are shaped to provide astigmatism correction at a marked axis denoted with dots on the surface of the lens. The lenses are rotated to the desired target axis after placement in the lens capsular bag during surgery. Sometimes the lenses rotate out of place after the surgery, which reduces the effectiveness of astigmatism correction.

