11.0 Statistical/Data Analysis Plan

11.1 Statistical Considerations:

List the statistical methods to be used to address the primary and secondary objectives, specific aims, and/or research hypotheses. Explain how missing data and outliers will be handled in the analysis. The analysis plan should be consistent with the study objectives. Include any subgroup analyses (e.g., gender or age group). Specify statistical methods and variables for each analysis. Describe how confounding variables will be controlled in the data analysis

The primary outcome and dependent variable will be the degree of toric rotation away from the target axis, and the time point of primary endpoint analysis will be when data for the last repeated measurement at 6 months has been obtained. The main treatment effect is a control group receiving a toric IOL only (Group 1) and a treatment group receiving a toric IOL plus capsular tension ring (Group 2). The statistical null hypotheses is as follows:

H01 — there is no difference in means of the degree of toric rotation away from the target axis between control and treatment groups

Subjects will be a random sample of left or right eyes of male and female patients seen in one Air Force medical treatment facility. The patients are presumed to be randomly selected from the population of patients obtaining similar care at this and other Air Force medical treatment facilities.

The study is organized as a mixed effects, randomized design. Subject (eye) is a random effect, as the patients whose eyes are the subjects of this study are presumed to have been randomly elected to obtain this treatment from the population of patients obtaining similar care at these Air Force medical treatment facilities, and the eyes are randomly assigned to treatment or control groups. Treatment is a fixed effect, as the effect of the intraocular lens and capsular tension ring cannot be generalized to other brands of toric intraocular lens or capsular tension rings.

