Reference 5 states eyes treated with a CTR rotated a mean 1.85°(1.72 SD) and eyes without a CTR rotated a mean 4.02°(2.04 SD). The minimum clinically significant difference of toric rotation away from the target axis the researchers wish to detect in this study is 1.85°. Using these parameters, a priori power for a repeated measures n analysis of variance (rANOVA) was assessed using G*Power Version 3.1.9.3. (12). The results indicate 50 subjects (eyes) will have a power of 0.957 at $\alpha = 0.05$ to detect this minimum clinically significant difference between the treatment groups.

Total sample and treatment group means, standard deviations, medians, interquartile ranges (IQR) and ranges will be calculated for interval variables. Frequency distributions will be produced for nominal and ordinal variables. Visual acuity, toric power, intended toric axis, and other variables will be included in the analysis.

The null hypothesis, H01, will be tested by a mixed effects repeated measures analysis of variance (rANOVA) using a general linear model, $y_{ij} = \mu + \alpha_i + \beta_j + \gamma_{ij} + \epsilon_{ij}$, where μ is the main treatment effect, α_i is time of repeated measure, and β_j represents the influence of individual j on his/her repeated observations.

[name], Senior Research Biostatistician Subject Matter Expert for Clinical Research Management under contracts OMNI 0004 3-82 and OMNI 0005 3-126, is the statistical consultant supporting this study. Statistical analysis will be performed with R Version 3.5.1. (13)

11.2 Sample Size:

50 eyes (approximately 25 eyes in each group) -- We are enrolling by number of eyes. If subjects have one eye that meets enrollment criteria, then that eye will be randomized into the treatment or control group. If both eyes meet enrollment criteria, then each eye will be randomized independently.

11.3 Total number of subjects requested (including records and specimens):

50

11.4 If you are recruiting by study arm, please identify the arms of the study and how many subjects will be enrolled in each arm

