Subjects will be a random sample of left or right eyes of male and female patients seen in one Air Force medical treatment facility. The patients are presumed to be randomly selected from the population of patients obtaining care at this Air Force medical treatment facilities.

The study is organized as a mixed effects, randomized design. Subject (eye) is a random effect, as the patients whose eyes are the subjects of this study are presumed to have been randomly elected to obtain this treatment from the population of patients obtaining similar care at these Air Force medical treatment facilities, and the subjects (eyes) are randomly assigned to treatment or control groups. Treatment is a fixed effect, as the effect of the intraocular lens and capsular tension ring cannot be generalized to other brands of toric intraocular lens or capsular tension rings.

Reference 5 states eyes treated with a CTR rotated a mean 1.85°(1.72 SD) and eyes without a CTR rotated a mean 4.02°(2.04 SD). The minimum clinically significant difference of toric rotation away from the target axis the researchers wish to detect in this study is 1.85°. Using these parameters, a priori power for a repeated measures n analysis of variance (rANOVA) was assessed using G*Power Version 3.1.9.3. (12). The results indicate 50 subjects (eyes) will have a power of 0.957 at $\alpha = 0.05$ to detect this minimum clinically significant difference between the treatment groups.

Total sample and treatment group means, standard deviations, medians, interquartile ranges (IQR) and ranges will be calculated for interval variables. Frequency distributions will be produced for nominal and ordinal variables.

The null hypothesis, H01, will be tested by a mixed effects repeated measures analysis of variance (rANOVA) using a general linear model, $y_{ij} = \mu + \alpha_i + \beta_j + \gamma_{ij} + \epsilon_{ij}$, where α is the main treatment effect, β is time of repeated measure, and γ_{ij} represents the influence of individual i on his/her repeated observations.

[name], Senior Research Biostatistician Subject Matter Expert for Clinical Research Management under contracts OMNI 0004 3-82 and OMNI 0005 3-126, is the statistical consultant supporting this study. Statistical analysis will be performed with R Version 3.5.1. (13)

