Eyes treated with capsular tension rings may experience less risk of the toric lens rotating out of its intended alignment. This would lead to an improvement in refractive outcome and may reduce their dependence on glasses postoperatively. They may also have a reduced risk of undergoing a second surgery to adjust the position of the toric intraocular lens. None of these benefits are guaranteed.

14.5 Privacy for Subjects:

Describe the measures to protect subject's privacy during recruitment, the consent process, and all research activities, etc.

During the study, the research consents, HIPAA Authorization Documents, participant registration forms, identifiable Master Key, and any other study documents utilized during the study will be stored in a locked cabinet or electronically on a CAC-enabled government computer and password protected.

14.6 Incidental or Unexpected Findings:

Describe the plan to address incidental findings and unexpected findings about individuals from screening to the end of the subject's participation in the research. In cases where the subject could possibly benefit medically or otherwise from the information, state whether or not the results of screening, research participation, research tests, etc., will be shared with subjects or their primary care provider. State whether the researcher is obligated or mandated to report results to appropriate military or civilian authorities and explain the potential impact on the subject

If significant new findings develop during the course of this study that may relate to subjects' decision to continue to participate in the study, they will be informed and/or their PCM will be notified.

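### Section 13.6 removes randomised eyes from the analysis for events after randomisation; complication eyes lose every reading, and the net direction of the bias is unknown

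*Combined protocol and SAP*

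**What the plan says.** Section 13.6 sorts complications by timing. A problem noted before ring insertion discontinues the patient. The eye stays enrolled, to characterise safety, "if intraoperative complications occur DURING OR AFTER the point of possible capsular tension ring insertion". The paragraph then adds: "This includes secondary surgical interventions such as repositioning of the IOL. These eyes will not be included in the data analysis after this point".

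The analysis plan neither carries nor corrects this rule. The primary outcome in 11.1 is "the degree of toric rotation away from the target axis", measured repeatedly to month 6. The null hypothesis "will be tested by a mixed effects repeated measures analysis of variance (rANOVA) using a general linear model" (11.1 and 11.6), with the eye as a random effect. No analysis population is named. The form's prompt at 11.1 reads "Explain how missing data and outliers will be handled in the analysis", and the text below it does not answer.

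Other sections bear on the point:

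- 16.1 repeats that these eyes stay enrolled but does not mention the exclusion. 10.1 keeps subjects in follow-up to month 6 however many visits they miss.
- 14.4 says of ring eyes: "They may also have a reduced risk of undergoing a second surgery to adjust the position of the toric intraocular lens".
- 14.1 names placement of the ring in the wrong part of the eye as a risk specific to the device.
- 10.1 has the envelope opened after lens removal, before the ring would be inserted.
- 12.5 and 12.6 make zonular or capsular problems seen at the moment of insertion a ground for exclusion.

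**The concern.** The rule selects eyes on events that follow randomisation, in two different ways.

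**Complications during or after possible insertion.** An intraoperative event precedes the day 1 photograph, so on any reading of the rule the eye contributes nothing and no model can recover it. Some such events can happen in either arm. Ring misplacement can happen only in ring eyes. The arms compared are then no longer the arms randomised.

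**Repositioning.** This is done because the lens has rotated, so removal depends on the primary outcome. If the ring reduces rotation, more control eyes than ring eyes would be affected.

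The phrase about the point after which eyes leave is also undefined. It can mean the event itself, so that earlier visits stay. But the only point the paragraph names is possible ring insertion, and on that reading the whole eye goes. The two readings give different data sets, and with about 25 eyes per arm a single eye is visible in the mean.

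Finally, an eye can be discontinued for a pre-insertion problem after its allocation has been revealed, and no tabulation of such eyes by arm is planned.

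**Working it through.** **Inputs from the documents.** Rotation is 1.85 (SD 1.72) degrees with a ring and 4.02 (SD 2.04) without (11.1), a difference of 2.17. There are about 25 eyes per arm (11.2). On the target, 11.1 says: "The minimum clinically significant difference of toric rotation away from the target axis the researchers wish to detect in this study is 1.85" degrees. Section 9.2 says of a rotation of 10 (printed as a percentage, read here as degrees): "This generally negates the benefit of the toric lens, requiring correction for the refractive error". No repositioning threshold or complication rate is given. Ten degrees is the only value with any anchor; 7.5 and 5 are assumptions that show the range.

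**The plan's own power.** Pooled SD = √((1.72² + 2.04²)/2) = 1.887, and f = 1.85/(2 × 1.887) = 0.490. For the between-arm test with m visits and within-eye correlation ρ, λ = f² × 50 × m/(1 + (m − 1)ρ) on F(1, 48). With an assumed ρ of 0.8, m = 4 gives λ = 14.14 and power 0.958; m = 5 gives 14.31 and 0.960. The stated 0.957 is therefore reproduced if ρ is near 0.8. It counts all 50 eyes.

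**Repositioned eyes, if whole eyes were dropped.** Take a gamma distribution with shape k = (mean/SD)² and scale θ = SD²/mean: control k = 3.883, θ = 1.035; ring k = 1.157, θ = 1.599. Eyes above the trigger t are removed, and the mean of the rest is mean × G(t; k + 1, θ)/G(t; k, θ), where G is the gamma distribution function.

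| Trigger | Removed per 25, control v ring | Chance none of 50 removed | Means left, control v ring | Difference | Change from 2.17 |
|---|---|---|---|---|---|
| 10 | 0.29 v 0.07 | 70% | 3.93 v 1.82 | 2.11 | −3% |
| 7.5 (assumed) | 1.57 v 0.32 | 14% | 3.69 v 1.75 | 1.93 | −11% |
| 5 (assumed) | 6.75 v 1.47 | under 0.1% | 3.03 v 1.55 | 1.48 | −32% |

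A lognormal model gives 2.10, 1.95 and 1.54. Only the 5-degree case falls below 1.85, and it needs 27% of control eyes to be repositioned (6.75/25). For scale, one control eye at 10 degrees among 24 averaging 4.02 carries (10 − 4.02)/25 = 0.24 degrees of the control mean, or 13% of 1.85. That is one realised eye, not an expected bias.

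**Repositioned eyes, if earlier visits stay.** Five visits were simulated with a random eye intercept, visit and arm-by-visit terms and an assumed reading error of SD 0.5; the triggering reading was kept. The month 6 difference is 2.18 with all eyes.

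- Stable rotation: 2.18 at every trigger.
- Rotation accruing as 60/90/95/100/100% of its final value: 2.17, 2.12 and 1.97 at 10, 7.5 and 5 degrees.
- Slower accrual, 30/60/80/90/100%: 2.17, 2.11 and 1.91.

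The worst case is 1 − 1.91/2.18, about 12%. The accrual curves are assumed.

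**Error rates with whole eyes dropped.** These are for a two-sided pooled t-test on month 6 rotation under the gamma model, at triggers of 10, 7.5 and 5. With no true effect, rejection is about 0.05 at every trigger. With a true 2.17, power is 0.98, 0.98 and 0.97, against 0.97 with all eyes. With a true 1.85 it is 0.93, 0.93 and 0.88, against 0.92.

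**Complication eyes.** Assume the remaining eyes have the 11.1 means and complication eyes rotate R degrees; dropping them always returns 2.17.

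- Assumed 4% of control and 8% of ring eyes, R = 10: full difference = (0.96 × 4.02 + 0.04 × 10) − (0.92 × 1.85 + 0.08 × 10) = 4.26 − 2.50 = 1.76, so 2.17 overstates it by about 24%. At R = 20 the full difference is 1.36 and the overstatement about 60%.
- Assumed 8% of control and 4% of ring eyes: the full difference is 2.32 at R = 10 and 2.72 at R = 20, so 2.17 understates it by about 7% and 20%.

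The sign depends on rates that the documents do not give.

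**The case against.** The strongest reply is that whole-eye deletion is a poor reading for repositioned eyes. No axis reading exists before day 1, so if the undefined point were ring insertion, the words limiting the exclusion to what comes after it would do no work. They make sense if they mean after the event. On that reading, a primary model that stops at repositioning is close to what the plan already intends. This stands.

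A second reply is that nothing in the documents plans a complete-case analysis: the model is mixed-effects with the eye as a random effect. This also stands. Silence on missing data leaves that route open but does not establish it.

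Third, the anchored effect is small. Section 9.2 speaks of refractive correction at 10, not surgery, and even whole-eye deletion there is expected to remove 0.36 eyes of 50 (0.29 + 0.07). This too stands.

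Fourth, adverse events are documented individually and reviewed by the Research Monitor (16.1, 18.4). That is true, but no comparison by arm is stated.

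A reader might infer that the rule as a whole understates the ring's benefit. The documents do not support that. The direction holds only for repositioned eyes, only if the ring works, and has appreciable size mainly under whole-eye deletion. Losses from ring complications can push the other way. Nor do repositioning losses give ground for a claim of inflated type I error.

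None of these replies reaches the complication eyes, which lose all their readings on either reading of the sentence.

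**Conclusion.** The concern holds in limited form. Section 13.6 states an exclusion rule that breaks the randomised comparison, and nothing in section 11 repairs it. For complication eyes the loss is complete and, for ring misplacement, one-sided; its direction and size cannot be derived from the documents. For repositioned eyes the natural reading costs little in a mixed model: under 1% at 10 degrees, and about 10% to 12% only at an assumed 5-degree trigger with rotation accruing over visits. Whole-eye deletion would understate a real effect by about 3% at 10 degrees and by 11% and 32% at the assumed 7.5 and 5. Power falls noticeably only at 5 degrees with a true difference of 1.85. The harm is therefore mainly to the estimate. These sizes rest on assumed triggers, distribution shapes and accrual curves. The point should be fixed before outcomes are seen by arm; it does not invalidate the design.

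**What to change.** In 13.6, delete the final sentence, the one that takes these eyes out of the data analysis. Add to 11.1 and 11.6:

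> All randomised eyes that continue in the study past the point of possible ring insertion are analysed in their randomised arm with a linear mixed model on all available readings; an eye with missing visits is not dropped. Eyes with a complication during or after that point contribute all their postoperative axis readings. Repositioned eyes contribute all readings up to repositioning, including the last axis documented before it; later readings are not used in the primary model. One sensitivity analysis carries the last pre-repositioning axis forward. Complications, repositioning, eyes left without a toric IOL and discontinued eyes, including those discontinued after the envelope was opened, are reported by arm.

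Sections 12.5 and 12.6 (problems at the moment of insertion exclude the eye) and 13.6 (complications during that step leave it enrolled) must be reconciled.

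The cost is wording and slight extra analysis. Affected eyes are already followed, 10.1 already allows extra photographs at unscheduled visits, and 10.2 already has the axis charted at the slit lamp. Two limits remain. Pre-event readings may understate later rotation in repositioned eyes. Eyes discontinued between envelope opening and insertion are reported, not analysed. For repositioned eyes the change mostly confirms the natural reading; the main gain is keeping complication eyes and ruling out whole-eye deletion.
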